5.4.1.1. Permanent Treatment Discontinuation

Treatment with IP must be discontinued by the investigator (who may consult the medical monitor) for any of the following conditions:

- a. any opportunistic infection, defined at the discretion of the investigator;
- b. any serious infection that requires antimicrobial therapy or hospitalization, or any infection that meets SAE reporting criteria;
- c. febrile neutropenia (temperature $>38.3^{\circ}\text{C}$ or a sustained temperature of 38°C for more than 1 hour) with absolute neutrophil count of $<1000/\text{mm}^3$;
- d. symptomatic anemia (e.g. signs/symptoms including pallor, shortness of breath, new heart murmur, palpitations, lethargy, fatigue) with hemoglobin $<7.5\text{ g/dL}$, or if transfusion is indicated regardless of hemoglobin value;
- e. complicated herpes zoster infection (with multi-dermatomal, disseminated, ophthalmic, or central nervous system involvement);
- f. evidence of active hepatitis C virus (HCV) during the study, as evidenced by HCV RNA positivity;
- g. evidence of active hepatitis B virus (HBV) during the study, as evidenced by HBV DNA positivity;
- h. any thromboembolic event that meets SAE reporting criteria;
- i. unacceptable toxicity or toxicity that, in the judgment of the investigator, compromises the subject's ability to continue study-specific procedures or is considered to not to be in the subject's best interest;
- j. subject's request to discontinue for any reason;
- k. subject's noncompliance;
- l. pregnancy;
- m. subject's use of prohibited concurrent therapy;
- n. laboratory criteria: After becoming aware of any of the below described abnormal laboratory changes occurring at any one time, an unscheduled visit (i.e. sequential visit) should occur to retest within 3 to 7 days (except creatinine, which should be retested 7 to 14 days apart).
 - 2 sequential platelet counts $<75000\text{ platelets/mm}^3$ (SI $<75.0 \times 10^9\text{ cells/L}$);
 - 2 sequential aspartate aminotransferase (AST) or alanine aminotransferase (ALT) >3 times the upper limit of normal range (ULN) and at least 1 of the following confirmed values:
 - total bilirubin $>2\times\text{ULN}$;
 - or international normalized ratio (INR) >1.5 ;
 - or accompanied by symptoms consistent with hepatic injury.

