For any subject with an initial AST or ALT elevation $>3\times\text{ULN}$, at the time of the second confirmatory blood draw, INR, prothrombin time (PT) and partial thromboplastin time (PTT) must also be assessed.

- 2 sequential AST or ALT elevations >5x ULN;
- 2 sequential values for estimated creatinine clearance (CrCl) <35 mL/min based on the Cockcroft-Gault formula¹.
- o. disease worsening (refer to Section 5.4.1.3);
- p. nonresponse to re-escalation therapy (refer to Section 5.1).
- q. subjects diagnosed with malignancy during the study except successfully treated non-melanoma skin cancer or cervical carcinoma in situ.

Any subject who discontinues study treatment, regardless of reason, will be invited to remain in the study and complete the visits as scheduled up to Week 48.

When the subject is discontinued from the study, the subject will be requested to return for the ED visit.

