Given this study will be performed during a severe acute respiratory syndrome coronavirus 2 (SARS-CoV-2) pandemic, appropriate measures should be taken to minimize the risk of SARS-CoV-2 infection for subjects participating in the study as well as study site personnel. Local guidelines to prevent SARS-CoV-2 infection should be adhered to.

HBV Surveillance

- Subjects with positive HBV surface antigen (HBsAg) at screening were excluded from the parent UC studies (GS-US-418-3898 and GS-US-418-3899). Subjects who were positive for HBV surface antibody (HBsAb), but negative for both HBsAg and HBV core antibody (HBcAb) at screening were eligible to participate in the parent UC studies (GS-US-418-3898 and GS-US-418-3899) and are also eligible to participate in the present study.
- Subjects with positive HBcAb and HBV DNA below the lower limit of quantification (LLOQ) in a parent UC study will require ongoing HBV DNA monitoring every 12 weeks during the present study. After study primary analysis endpoint unblinding frequency will be reduced to every 24 weeks. These subjects may also require prophylactic treatment per investigator discretion in accordance with local guidelines/standard of care.
- Any subject who has HBV DNA \geq LLOQ will be discontinued from the present study (Section 5.4.1.1 and Section 6.2 item 10).

Malignancy has been reported in subjects on filgotinib. In the present study, subjects will be required to have up to date colorectal cancer screening and surveillance as per standard of care. Following SELECTION and SELECTION-LTE studies, subjects with recent malignancies will be excluded from the present study (Section 6.2, Item 9.1) and those diagnosed during the study will be discontinued, except successfully treated non-melanoma skin cancer or cervical carcinoma in situ.

Highly effective contraceptive measures are expected to mitigate the risk of fetal toxicity. Refer to Section 6.3.1 for further guidance on pregnancy precautions and contraceptive requirements.

For more details refer to the latest version of the IB and its relevant updates/addenda.

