6.2. Exclusion Criteria

Subjects meeting one or more of the following criteria cannot be selected for this clinical study.

Medical History and Concurrent Diseases

1. Any chronic medical condition (including but not limited to, cardiac or pulmonary disease, alcohol, or drug abuse) that, in the opinion of the investigator or sponsor would make the subject unsuitable for the study or would prevent compliance with the study protocol.

Previous and Concomitant Medications

2. Subject has taken any prohibited therapies before the planned first dose of IP.
3. Subject concurrently participates or participated in a drug, drug/device, or biologic investigational research study with the exception of the preceeding SELECTION-LTE study within 12 weeks or 5 half-lives of the IP, whichever is longer, prior to the first dose.

Allergies and Adverse Drug Reactions

4. Subject has a known hypersensitivity to filgotinib ingredients or history of a significant allergic reaction to filgotinib ingredients as determined by the investigator.

Other Exclusion Criteria

5. Female subject who is pregnant or breastfeeding, or intending to become pregnant or breastfeed, and/or plans to undergo egg donation or egg harvesting for the purpose of current or future fertilization, during the study and until the end of the study.
6. Criterion deleted per amendment 1.
7. Subject is unable or unwilling to comply with restrictions regarding prior and concomitant medication as described in the protocol.
8. Criterion modified per amendment 1.
 - 8.1 Subject has a positive QuantiFERON® TB test at screening or has 2 indeterminate QuantiFERON® TB test results that require IP treatment interruption, or subject has signs and symptoms of TB reactivation at screening.
9. Criterion modified per amendment 1.
 - 9.1 History of malignancy during or in the last 5 years prior to participation in the UC parent studies, except for subjects who have been successfully treated for nonmelanoma skin cancer or cervical carcinoma in situ.
10. Subject meets discontinuation criteria of the SELECTION-LTE study.
11. Investigator or other study staff or relative thereof who is directly involved in the conduct of the study.
12. Subject has any condition or circumstances that, in the opinion of the investigator, may make a subject unlikely or unable to complete the study or comply with study procedures and requirements (e.g. active alcohol or drug abuse).

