8.3. Efficacy Assessments

8.3.1. Endoscopy and Biopsy Sample Collection

A sigmoidoscopy will be performed at the visits specified in the Schedule of Activities in Section 8.9.1.

The ES for randomization purposes will be obtained from a sigmoidoscopy performed during the screening period (including biopsy collection for histology assessment). It is recommended that the screening sigmoidoscopy be performed only after the subject meets all other eligibility criteria.

In case of a suspected UC flare, an additional sigmoidoscopy is needed (refer to Section 5.1).

Subjects who discontinue the study prior to Week 48 need a sigmoidoscopy at the ED visit.

The endoscopy will be assessed by a local reader and scored using the Mayo scoring system (refer to Section 8.3.2).

[REDACTED]

[REDACTED]

[REDACTED]

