EVENT	SCREENING PERIOD		TREATMENT PERIOD						FOLLOW-UP PERIOD	
	S1 ^a	S2	Day 1 ^b	W4	W12 and then every 12 weeks	W24 and then every 24 weeks	W48 ^c and then every 48 weeks	ED	EoT ^d	4 weeks after last IP dose (EoS)
	D-28 to D-1			± 3 days	± 7 days	± 7 days	± 7 days			± 3 days
Hematology		✓ ^{l, m}		✓	✓			✓	✓	✓
Chemistry		✓ ^{l, m}		✓	✓			✓	✓	✓
Lipid profile (fasted ⁿ)		✓ ^{l, m}				✓			✓	
Urine analysis		✓ ^{l, m}				✓			✓	
HBV DNA monitoring ^o		✓ ^l			✓				✓	
12-lead ECG		✓ ^l					✓		✓	
Serum immunoglobulin		✓ ^l				✓			✓	
CRP		✓ ^l		✓	✓			✓	✓	
Fecal calprotectin ^p	✓ ^q	✓ ^{l,r}		✓	✓			✓	✓	

^m Screening clinical laboratory results may only be available after randomization. In that case, these results will be reviewed after randomization and subjects with laboratory results meeting discontinuation criteria, will be discontinued from the study.

ⁿ Subjects should remain fasted for at least 8 hours, excluding water.

^o Only subjects with positive HBcAb and HBV DNA <LLOQ in a parent UC study will require ongoing HBV DNA monitoring every 12 weeks during the present study, and after study primary endpoint unblinding every 24 weeks.

^p Stool samples need to be taken prior to bowel preparation for endoscopy. Stool samples can be collected within 24 hours prior to the visit or during the visit.

^q FCP should be assessed during screening if the last assessment during SELECTION-LTE was >6 months prior to screening or the most recent value was >250 µg/g.

^r This FCP assessment should be obtained at the EoT visit in SELECTION-LTE (i.e. performed after the subject is fully eligible to roll over to the present study) and will be the baseline of the present study. In case FCP was not obtained at the EoT visit of SELECTION-LTE, an unscheduled stool sample should be collected within 24 hours prior to or during Day 1 (i.e. predose).

EVENT	SCREENING PERIOD		TREATMENT PERIOD						FOLLOW-UP PERIOD	
	S1 ^a	S2	Day 1 ^b	W4	W12 and then every 12 weeks	W24 and then every 24 weeks	W48 ^c and then every 48 weeks	ED	EoT ^d	4 weeks after last IP dose (EoS)
Study Day (D)/ Week (W)	D-28 to D-1			± 3 days	± 7 days	± 7 days	± 7 days			± 3 days
e-Diary instruction & review ^u			✓	✓	✓			✓	✓	✓
modified Mayo Clinical Score ^w	✓						✓	✓		

^a For subjects who consent to participate in the optional PK substudy, PK blood samples will be collected either at the Week 4 or Week 12 visit, or if more convenient, at any

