9.2.3. Full Analysis Set

All randomized subjects who have received at least 1 dose of IP.

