9.3.4.1. Analysis for Primary Efficacy Endpoint

9.3.4.1.1. Primary Efficacy Estimand

The primary estimand for the primary endpoint targets to estimate the effect of decreasing the filgotinib dose from 200 mg q.d. to 100 mg q.d. versus remaining on 200 mg q.d. on corticosteroid-free mMCS remission without ES-confirmed flare or discontinuation of treatment at Week 48, regardless of treatment interruptions, in subjects who are in stable clinical remission at study entry. The effect size will be estimated using the Mantel-Hanszel method and expressed as a difference in proportions.

The primary estimand for the primary endpoint is described according to the following attributes:

Primary Endpoint	Primary Estimand
Treatment	Filgotinib 100 mg q.d. and filgotinib 200 mg q.d. as randomized.
Population	Subjects who are in stable clinical remission on filgotinib 200 mg q.d. defined through the appropriate inclusion / exclusion criteria.
Variable	Binary corticosteroid-free mMCS remission without ES-confirmed flare and without discontinuation of treatment at Week 48. Corticosteroid-free is defined as free of corticosteroids for at least 12 weeks.
Intercurrent events including strategy for addressing them	
ES-confirmed UC flare: Subjects randomized to the filgotinib 100 mg q.d. or 200 mg q.d. group will be considered as nonresponders for any visit after the re-escalation visit, for flares occurring prior to Week 48 (Composite strategy).Permanent treatment discontinuation: Subjects who discontinue treatment prior to Week 48 will be considered as nonresponders in both the 100 mg q.d. and the 200 mg group q.d. (Composite strategy).Any temporary treatment interruption: Data collected for subjects who temporarily interrupt treatment will be included as reported in the analysis (Treatment policy strategy).
Population-level summary	The treatment difference in the percentage of subjects meeting corticosteroid-free mMCS remission criteria between the filgotinib 100 mg q.d. group and 200 mg q.d. group at Week 48.
Estimator	The adjusted proportion difference (filgotinib 200 mg – filgotinib 100 mg) with corresponding 95% CI as calculated by a stratified Mantel-Haenszel test (stratification factor: baseline ES [0 or 1]).

Details on sensitivity analyses for the primary estimand will be described in the SAP.

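### Footnote m of the visit schedule removes subjects with late-read screening labs from the study, whereas Section 5.4.1.1 stops treatment and keeps follow-up to Week 48: a real conflict with a small effect

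*Protocol*

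**What the plan says.** Four rows of the schedule in Protocol 8.9.1 carry footnote m at the second screening visit: hematology, chemistry, lipid profile and urine analysis. The footnote allows these results to be unavailable at randomization and then says "these results will be reviewed after randomization and subjects with laboratory results meeting discontinuation criteria, will be discontinued from the study". It does not name the criteria and mentions no retest. SAP 2.4.1 reproduces it.

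Protocol 5.4.1.1 introduces its list, in which item n holds the laboratory criteria, with "Treatment with IP must be discontinued by the investigator (who may consult the medical monitor) for any of the following conditions". Item n asks for a retest at 3 to 7 days (7 to 14 days for creatinine). The section then states: "Any subject who discontinues study treatment, regardless of reason, will be invited to remain in the study", with visits continuing as scheduled up to Week 48. Leaving the study is covered by a separate sentence, with its own early discontinuation (ED) visit.

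The full analysis set (FAS, Protocol 9.2.3) is "All randomized subjects who have received at least 1 dose of IP". For the primary estimand, Protocol 9.3.4.1.1 says "Subjects who discontinue treatment prior to Week 48 will be considered as nonresponders". The secondary estimand of the same endpoint (9.3.4.1.2) and those of IBDQ, CRP and FCP (9.3.4.2.1) use data collected after permanent treatment discontinuation.

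**The concern.** The protocol treats stopping drug and leaving the study as different acts. Footnote m prescribes the second where 5.4.1.1 prescribes the first.

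The timing allows an affected subject to be dosed already. Screening visit 2 and Day 1 may fall on the same or consecutive days (8.9.1), and study drug starts on Day 1, or on Day 2 if the parent-study dose was already taken (7.2). One dose puts the subject in the FAS. Footnote m therefore ends follow-up without taking the subject out of the analysis.

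At stake is information that the treatment-policy estimands ask for. If it is not collected, the protocol substitutes nonresponse at Week 48 for mMCS remission, last observation carried forward for IBDQ, and a missing-at-random assumption in the mixed model for CRP and FCP. A subject not yet dosed is outside the FAS and raises no such problem.

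**Working it through.** **The plan's precision figure.** Protocol 9.1 gives a worst-case 95% CI half-width of 22.5 points for 40 per group, by the continuity-corrected Newcombe method. At 20/40 versus 20/40 the corrected Wilson lower limit is (40 + 3.8415 − 1 − 1.96 × √43.8165) / 87.683 = 0.3406, which is 0.1594 below 0.5. The limits are symmetric, so the half-width is √2 × 0.1594 = 0.2254, or 22.5 points. The figure reproduces and serves as the yardstick below.

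**What a dosed subject contributes under each rule:**

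| Analysis | Follows 5.4.1.1 and accepts the invitation | Follows footnote m |
|---|---|---|
| Primary estimand (composite) | Nonresponder | Nonresponder |
| Secondary estimand, mMCS remission | Observed Week 48 status | Missing, so nonresponder |
| Secondary estimand, IBDQ | Observed at Week 48 | LOCF |
| Secondary estimand, CRP and FCP | Observed by visit | Missing at random in the model |

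The primary estimand is identical in both columns.

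**Loss per subject, secondary remission estimand, 40 per arm.** The documents give none of the needed rates. Assume off-treatment remission at Week 48 of q = 20% to 60% and acceptance of the invitation of a = 50% to 100%. The loss in an arm's rate is q × a / 40:

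- smallest: 0.20 × 0.5 / 40 = 0.25 points
- largest: 0.60 × 1 / 40 = 1.5 points

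**Expected change in the treatment difference.** The labs are drawn before the first study dose, so being caught does not depend on arm. Assume remission of 80% versus 60% in the other subjects, one affected subject per arm, and the same q in both arms:

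- followed: (39 × 0.80 + q)/40 − (39 × 0.60 + q)/40 = 7.8/40 = 19.5 points
- imputed: (39 × 0.80)/40 − (39 × 0.60)/40 = 7.8/40 = 19.5 points

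The change is 0.

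**Chance imbalance.** Take k affected subjects, each equally likely to be in either arm and each with probability q × a of a remission that follow-up would have recorded. The SD of the shift is √(k × qa)/40, with qa from 0.20 × 0.5 = 0.10 to 0.60 × 1 = 0.60:

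| k (assumed) | qa = 0.10 | qa = 0.60 |
|---|---|---|
| 1 | 0.79 points | 1.94 points |
| 4 | 1.58 points | 3.87 points |

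**Terminated-study SAP.** SAP 2.4.3 gives 22 randomized. Assuming about 11 per arm, one removed subject lowers that arm's CRP/FCP count by 1/11 = 9.1% and raises the standard error by √(11/10) − 1 = 4.9%, at the visits the subject would have reached. SAP 6.3.2 excludes only biomarker data after confirmed flare, so values after a treatment stop would count. The Week 4 window in SAP Table 3 opens on Day 15, so CRP or FCP taken at an ED visit on Days 2 to 14 falls in no window.

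**The case against.** The strongest defence is that footnote m is a deliberate rule for subjects who should not have been enrolled. It concerns screening results, and exclusion 10 bars anyone for whom "Subject meets discontinuation criteria of the SELECTION-LTE study" holds, which is close to the footnote's own term. The protocol also prescribes study discontinuation elsewhere, for active tuberculosis (5.4.1.2). This reading is possible, but the footnote does not state it and 5.4.1.1 makes no exception for late-detected ineligibility. A dosed subject would remain in the FAS in any case. Which criteria are meant is a matter of missing detail; the parent study's criteria are not in these documents.

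Several points about weight stand. The numeric laboratory criteria in 5.4.1.1 need repeated or confirmed values, and lipids and urinalysis have no threshold there, so few subjects would qualify. Staying on is only an invitation. The SAP replaces the planned estimands (SAP 3), imputes nothing for data missing because the study stopped (4.4.1.2), and lists the primary endpoint and IBDQ (6.1). SAP 6.1 also says that no subject had reached Week 48.

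A reader might infer more than the documents support:

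- **That the primary result is biased.** It is not, because a treatment stop is nonresponse either way.
- **That data were in fact lost.** No document shows that even one subject was affected.
- **That the secondary remission rate could fall by 1/40 to 4/40, or 2.5 to 10 points.** That requires one to four affected subjects all in one arm, each certain to be in remission at Week 48. It is a worst case, not an expectation.
- **That hepatitis B monitoring falls under the same footnote.** The HBV DNA row does not carry footnote m. Section 5.5 says that subjects with quantifiable HBV DNA "will be discontinued from the present study (Section 5.4.1.1 and Section 6.2 item 10"), which is similarly loose wording but a separate matter.

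**Conclusion.** The conflict is literal and in current text, and the point stands as minor. For a subject already dosed, footnote m would end follow-up that 5.4.1.1 offers and that the treatment-policy secondary estimands use. As planned, the cost is 0.25 to 1.5 points of an arm's rate per affected subject, an expected change of about zero in the treatment difference, and a chance shift with an SD of 0.8 to 3.9 points for one to four subjects. These figures rest on assumed counts, off-treatment remission and acceptance, and on affected subjects falling in either arm with equal chance. Under the terminated-study SAP, nothing beyond the descriptive CRP/FCP tables can be affected.

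**What to change.** In Protocol 8.9.1, and in the copy in SAP 2.4.1, reword footnote m to say that subjects meeting the laboratory criteria of Section 5.4.1.1, including the required retest, will be discontinued from study treatment and, if already dosed, invited to remain in the study up to Week 48. This applies the protocol's existing rule, names the criteria and needs no new procedure.

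The cost is wording in one footnote in two documents, plus up to five off-treatment visits (Weeks 4, 12, 24, 36 and 48) for a subject who accepts. Section 8.3.1 already requires an endoscopy of those who leave early: "Subjects who discontinue the study prior to Week 48 need a sigmoidoscopy at the ED visit". For a subject who stays, the Week 48 sigmoidoscopy takes its place. No stated sample-size or precision figure changes.

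Aligning the HBV DNA sentence in 5.5 with 5.4.1.1 is a separate, optional consistency edit.

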8.9.2. Schedule of Activities After Re-escalation

Event	TREATMENT PERIOD					After Week 12: Continue with the regular Schedule of Activities, starting with assessments of the next 12-weekly visit until end of the study
	baseline	W2 ^a	W4	W8	W12	
Study Day (D)/ Week (W)		± 3 days	± 3 days	± 7 days	± 7 days	
Physical examination (symptom-directed)	✓		✓	✓	✓	
Vital signs	✓		✓	✓	✓	
Weight	✓		✓	✓	✓	
Hematology	✓		✓	✓	✓	
Chemistry	✓		✓	✓	✓	
Urine pregnancy test ^b	✓		✓	✓	✓	
CRP	✓		✓	✓	✓	
e-Diary instruction & review	✓	✓	✓	✓	✓	

^a Phone contact^b Only for women of childbearing potential

Event	TREATMENT PERIOD					
	baseline	W2 ^a	W4	W8	W12	
Study Day (D)/ Week (W)		± 3 days	± 3 days	± 7 days	± 7 days	After Week 12:
Dispense IP	✓		✓	✓	✓	12-weekly visit until end of the study
Concomitant medications	✓	✓	✓	✓	✓	
Dose IP	q.d. starting from dispensing of unblinded re-escalated IP ^c					
AE assessments	throughout the study					

AE: adverse event; CRP: C-reactive protein; [REDACTED] q.d.: once daily.

^c If the subject has already taken IP on the re-escalation baseline day, the first adjusted dose should be taken on Day 2 of re-escalation.

